4.3. DESCRIPTION OF TREATMENTS

The following IMPs will be used in the study:

- Arm A: Combo Target (LGX818 450 mg p.o. od + MEK162 45 mg p.o. bid) until PD; then Combo Immuno (nivolumab 1 mg/kg solution i.v.combined with ipilimumab 3 mg/kg solution i.v.every 3 weeks for 4 doses then nivolumab 3 mg/kg solution i.v.every 2 weeks) until PD.
- Arm B: Combo Immuno (nivolumab 1 mg/kg solution i.v.combined with ipilimumab 3 mg/kg solution i.v.every 3 weeks for 4 doses then nivolumab 3 mg/kg solution i.v.every 2 weeks) until PD; then Combo Target (LGX818 450 mg p.o. od + MEK162 45 mg p.o. bid) until PD.
- Arm C: Combo Target (LGX818 450 mg p.o. od + MEK162 45 mg p.o. bid) for 8 weeks followed by Combo Immuno (nivolumab 1 mg/kg solution i.v.combined with ipilimumab 3 mg/kg solution i.v.every 3 weeks for 4 doses then nivolumab 3 mg/kg solution i.v.every 2 weeks) until PD; then Combo Target (LGX818 450 mg p.o. od + MEK162 45 mg p.o. bid) until PD.

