23.2. DERMATOLOGICAL EXAMINATION

Dermatological examinations will be analyzed on the SAF set.

According to study protocol, this examination will be performed at each baseline visit and every 8 weeks.

Descriptive summaries of the following parameters will be provided for each visit by treatment arm:

- Dermatological examination performed (No, Yes);
- Result of the dermatological examination (Normal, Abnormal);
- If Results is Abnormal, Diagnosis (Squamous cell carcinoma, Keratoacanthomas, Other pathology findings)
- Evidence of severe or uncontrolled systemic disease or concurrent undesirable condition (No, Yes)

A line listing of dermatological examinations during the study will be provided.

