24. TABLE SHELLS AND SPECIFICATIONS

24.1. TABLE SPECIFICATIONS

Tables will be provided as defined by the table shells.

Similar tables based on different populations will have the same number, except for the last digit.

All output will be generated by SAS and exported into a RTF format and then convert to PDF format. All output will be in landscape orientation. Font size will be Courier New 8 pt.

The header containing the sponsor' name (Fondazione Melanoma (ONLUS)) and protocol number will appear on the top left corner of each page of the output. The page number, in the format of "Page x of y", will appear on the top right corner of the output, where y = last page of corresponding output.

Column headers in tables include the total possible numbers to be included in summaries for that table, designated as "(N=XX)".

The SAS program name, and the date and time of the creation of the output (run date) will appear on the bottom left corner as follows:

Source: [program name].sas, Run on ddmmyyyy

Table Format Specification:

Maximum and minimum values will be reported with the same number of decimal places as collected. Means and medians will be reported to one additional decimal place. Standard deviations and standard errors will be reported to two decimal places more than the collected data. Percentages will be reported with one decimal place.

Data in the tables are formatted as follows:

- Text fields in the body of the tables and listings will be left-justified.
- When no data are available for a table, an empty page with the title will be produced with suitable text. Example: THERE WERE NO SERIOUS ADVERSE EVENTS.

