	Min/Max	xx/xx	xx/xx
Follow-up	n	xx	xx
	Mean (SD)	xx.x (x.x)	xx.x (x.x)
	Median	xx.x	xx.x
	Min/Max	xx/xx	xx/xx

Notes:

(*) Change from baseline is calculated relative to Baseline 1 for values between Baseline 1 and Baseline 2; Baseline 2 for values between Baseline 2 and Baseline 3; Baseline 3 for values after Baseline 3. Change from baseline values include only those patients with both a Baseline value and a value for summarized time period.

n represents number of patients contributing to summary statistics.

Source: XXXX.SAS, Run on DDMMYYYY

TABLE 85. ECG Parameters - ARM A

POPULATION: SAF < Note for SAS Programmer: the following must be presented for QT, QRS, QTcB, cardiac axis, Ejection Fraction value as well >

	Statistic	Value	Change from Baseline (*)
PR interval (ms)			
Baseline 1	n	xx	
	Mean (SD)	xx.x (x.x)	
	Median	xx.x	
	Min/Max	xx/xx	
Week 4 - Combo Target	n	xx	xx
	Mean (SD)	xx.x (x.x)	xx.x (x.x)
	Median	xx.x	xx.x
	Min/Max	xx/xx	xx/xx
Week <Every 12 wks> - Combo Target	n	xx	xx
	Mean (SD)	xx.x (x.x)	xx.x (x.x)
	Median	xx.x	xx.x
	Min/Max	xx/xx	xx/xx
Baseline 2	n	xx	
	Mean (SD)	xx.x (x.x)	
	Median	xx.x	
	Min/Max	xx/xx	
Week 4 - Nivolumab + Ipilimumab	n	xx	xx
	Mean (SD)	xx.x (x.x)	xx.x (x.x)
	Median	xx.x	xx.x
	Min/Max	xx/xx	xx/xx
Week <Every 12 wks> - Nivolumab	n	xx	xx
	Mean (SD)	xx.x (x.x)	xx.x (x.x)
	Median	xx.x	xx.x
	Min/Max	xx/xx	xx/xx

Notes:

(*) Change from baseline is calculated relative to Baseline 1 for values between Baseline 1 and Baseline 2; Baseline 2 for values after Baseline 2. Change from baseline values include only those patients with both a Baseline value and a value for summarized time period. n represents number of patients contributing to summary statistics.

Source: XXXX.SAS, Run on DDMMYYYY

TABLE 86. ECG Parameters - ARM B

POPULATION: SAF < Note for SAS Programmer: the following must be presented for QT, QRS, QTcB, cardiac axis, Ejection Fraction value as well >

	Statistic	Value	Change from Baseline (*)
PR interval (ms)			
Baseline 1	n	xx	
	Mean (SD)	xx.x (x.x)	
	Median	xx.x	
	Min/Max	xx/xx	
Week 4 - Nivolumab + Ipilimumab	n	xx	xx
	Mean (SD)	xx.x (x.x)	xx.x (x.x)
	Median	xx.x	xx.x
	Min/Max	xx/xx	xx/xx
Week <Every 12 wks> - Nivolumab	n	xx	xx
	Mean (SD)	xx.x (x.x)	xx.x (x.x)
	Median	xx.x	xx.x
	Min/Max	xx/xx	xx/xx
Baseline 2	n	xx	
	Mean (SD)	xx.x (x.x)	
	Median	xx.x	
	Min/Max	xx/xx	
Week 4 - Combo Target	n	xx	xx
	Mean (SD)	xx.x (x.x)	xx.x (x.x)
	Median	xx.x	xx.x
	Min/Max	xx/xx	xx/xx

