Week <Every 12 wks> - Combo Target	n	xx	xx
	Mean (SD)	xx.x (x.x)	xx.x (x.x)
	Median	xx.x	xx.x
	Min/Max	xx/xx	xx/xx

Notes:

(*) Change from baseline is calculated relative to Baseline 1 for values between Baseline 1 and Baseline 2; Baseline 2 for values after Baseline 2. Change from baseline values include only those patients with both a Baseline value and a value for summarized time period. n represents number of patients contributing to summary statistics.

Source: XXXX.SAS, Run on DDMMYYYY

TABLE 87. ECG Parameters - ARM C

POPULATION: SAF < Note for SAS Programmer: the following must be presented for continuous values of URBC/HPF, Bacteria, Other as well >

	Statistic	Value	Change from Baseline (*)
PR interval (ms)			
Baseline 1	n	xx	
	Mean (SD)	xx.x (x.x)	
	Median	xx.x	
	Min/Max	xx/xx	
Week 4 - Combo Target	n	xx	xx
	Mean (SD)	xx.x (x.x)	xx.x (x.x)
	Median	xx.x	xx.x
	Min/Max	xx/xx	xx/xx
Baseline 2	n	xx	
	Mean (SD)	xx.x (x.x)	
	Median	xx.x	
	Min/Max	xx/xx	
Week 4 - Nivolumab + Ipilimumab	n	xx	xx
	Mean (SD)	xx.x (x.x)	xx.x (x.x)
	Median	xx.x	xx.x
	Min/Max	xx/xx	xx/xx
Week <Every 12 wks> - Nivolumab	n	xx	xx
	Mean (SD)	xx.x (x.x)	xx.x (x.x)
	Median	xx.x	xx.x
	Min/Max	xx/xx	xx/xx
Baseline 3	n	xx	
	Mean (SD)	xx.x (x.x)	
	Median	xx.x	
	Min/Max	xx/xx	
Week 4 - Combo Target	n	xx	xx
	Mean (SD)	xx.x (x.x)	xx.x (x.x)
	Median	xx.x	xx.x
	Min/Max	xx/xx	xx/xx
Week <Every 12 wks> - Combo Target	n	xx	xx
	Mean (SD)	xx.x (x.x)	xx.x (x.x)
	Median	xx.x	xx.x
	Min/Max	xx/xx	xx/xx

Notes:

(*) Change from baseline is calculated relative to Baseline 1 for values between Baseline 1 and Baseline 2; Baseline 2 for values between Baseline 2 and Baseline 3; Baseline 3 for values after Baseline 3. Change from baseline values include only those patients with both a Baseline value and a value for summarized time period.
n represents number of patients contributing to summary statistics.

Source: XXXX.SAS, Run on DDMMYYYY

TABLE 88. Cardiological Assessments - ARM A

POPULATION: SAF

< Note for SAS Programmer: the following must be presented for each visit during the study >

	Statistic	Arm A (N=XX)
<Visit n>		
ECG Result		
Normal	n (%)	xx (xx.x%)
Abnormal	n (%)	xx (xx.x%)
Interpretation of abnormality (*)		
Not clinically significant	n (%)	xx (xx.x%)
Clinically significant	n (%)	xx (xx.x%)
Type of LVEF scan		
ECHO	n (%)	xx (xx.x%)
MUGA	n (%)	xx (xx.x%)
Interpretation of ECHO/MUGA scan		
Normal	n (%)	xx (xx.x%)
Abnormal, NCS	n (%)	xx (xx.x%)
Normal, CS	n (%)	xx (xx.x%)

Notes:

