Dermatological Examination performed		
No	n (%)	xx (xx.x%)
Yes	n (%)	xx (xx.x%)
Result (*)		
Normal	n (%)	xx (xx.x%)
Abnormal	n (%)	xx (xx.x%)
Diagnosis (§)		
Squamous cell carcinoma	n (%)	xx (xx.x%)
Keratoacanthomas	n (%)	xx (xx.x%)
Other pathology findings	n (%)	xx (xx.x%)
Evidence of severe or uncontrolled systemic disease or concurrent undesirable condition		
No	n (%)	xx (xx.x%)
Yes	n (%)	xx (xx.x%)

Notes:

Percentages are calculated relative to the total number of patients of ARM A in the SAF set.

(*) Percentages are calculated relative to the total number of patients of ARM A in the SAF set who performed the dermatological examination.

(§) Percentages are calculated relative to the total number of patients of ARM A in the SAF set who resulted abnormal.

Source: XXXX.SAS, Run on DDMMYYYY

TABLE 101. Dermatological examination during the study - ARM B

POPULATION: SAF < Note for SAS Programmer: the following must be presented for each visit: Baseline 1, Q8W, Baseline 2, Q8W >

	Statistic	Arm B (N=XX)
<Visit n>		
Dermatological Examination performed		
No	n (%)	xx (xx.x%)
Yes	n (%)	xx (xx.x%)
Result (*)		
Normal	n (%)	xx (xx.x%)
Abnormal	n (%)	xx (xx.x%)
Diagnosis (§)		
Squamous cell carcinoma	n (%)	xx (xx.x%)
Keratoacanthomas	n (%)	xx (xx.x%)
Other pathology findings	n (%)	xx (xx.x%)
Evidence of severe or uncontrolled systemic disease or concurrent undesirable condition		
No	n (%)	xx (xx.x%)
Yes	n (%)	xx (xx.x%)

Notes:

Percentages are calculated relative to the total number of patients of ARM B in the SAF set.

(*) Percentages are calculated relative to the total number of patients of ARM B in the SAF set who performed the dermatological examination.

(§) Percentages are calculated relative to the total number of patients of ARM B in the SAF set who resulted abnormal.

Source: XXXX.SAS, Run on DDMMYYYY

TABLE 102. Dermatological examination during the study - ARM C

POPULATION: SAF < Note for SAS Programmer: the following must be presented for each visit: Baseline 1, Baseline 2, Q8W, Baseline 3>

	Statistic	Arm C (N=XX)
<Visit n>		
Dermatological Examination performed		
No	n (%)	xx (xx.x%)
Yes	n (%)	xx (xx.x%)
Result (*)		
Normal	n (%)	xx (xx.x%)
Abnormal	n (%)	xx (xx.x%)
Diagnosis (§)		
Squamous cell carcinoma	n (%)	xx (xx.x%)
Keratoacanthomas	n (%)	xx (xx.x%)
Other pathology findings	n (%)	xx (xx.x%)
Evidence of severe or uncontrolled systemic disease or concurrent undesirable condition		
No	n (%)	xx (xx.x%)
Yes	n (%)	xx (xx.x%)

Notes:

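### Shell Tables 87, 88-90 and 102 contradict SAP Sections 21.3 and 23.2: Arm C loses planned dermatology and ECG/ejection-fraction summaries, and one ECHO/MUGA category is mislabelled in all arms

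*Supplement*

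**What the plan says.** Table numbers here are those printed on the shells; the index at the start of Section 26 numbers the same tables two lower.

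- **Standing of the shells.** Section 24.1: "Tables will be provided as defined by the table shells".
- **Dermatology.** Section 23.2, citing the protocol, says "this examination will be performed at each baseline visit and every 8 weeks", with summaries for each visit by arm. The shells for Arms A and B (Tables 100 and 101) both say "the following must be presented for each visit: Baseline 1, Q8W, Baseline 2, Q8W". The Arm C shell (Table 102) says "the following must be presented for each visit: Baseline 1, Baseline 2, Q8W, Baseline 3".
- **Arm C treatment.** Under Section 4.3 the first Combo Target course is given "for 8 weeks followed by Combo Immuno". After progression on Combo Immuno the sequence ends with "then Combo Target (LGX818 450 mg p.o. od + MEK162 45 mg p.o. bid) until PD".
- **ECG and ejection fraction.** Section 21.3 plans summaries of PR, QT, QRS, QTcB, cardiac axis and ejection fraction, as values and changes from baseline, at each visit and by arm. The Arm A and B shells (Tables 85 and 86) display PR and add "the following must be presented for QT, QRS, QTcB, cardiac axis, Ejection Fraction value as well". The Arm C shell (Table 87) displays PR and adds "the following must be presented for continuous values of URBC/HPF, Bacteria, Other as well".
- **ECHO/MUGA interpretation.** Section 21.3 has three categories: normal, a clinically insignificant abnormality and a clinically significant one. Tables 88, 89 and 90 print them as 'Normal', 'Abnormal, NCS' and 'Normal, CS'.

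**The concern.** Toxicity is both a secondary and a safety objective, and Sections 21.3 and 23.2 commit to summaries by arm. If the shells are programmed literally, three things go wrong.

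1. Skin findings at the 8-weekly visits of Arm C's final Combo Target course, including the squamous cell carcinoma and keratoacanthoma rows, do not reach the dermatology table. The corresponding findings in Arms A and B do.
2. Arm C has no summary of QT, QRS, QTcB, cardiac axis or ejection fraction, or of their changes from baseline, to set beside those of the other arms.
3. A clinically significant abnormality on an ECHO/MUGA scan is counted, in every arm, in a row whose label begins with 'Normal'.

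**Working it through.** There is no sample size, power or alpha figure to reproduce. The check sets the SAP text against the shells and counts.

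**Dermatology visits (Section 4.3 against Tables 100-102)**

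| Arm | Treatment phases | Phases followed by an 8-weekly block in the shell |
|---|---|---|
| A | 2 | 2 |
| B | 2 | 2 |
| C | 3 | 1 (after Baseline 2) |

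Arm C therefore lacks the block in 3 − 1 = 2 phases. One of these is harmless. The first course lasts 8 weeks, so its week-8 examination falls at about Baseline 2, which Table 102 lists. That leaves 2 − 1 = 1 phase uncovered: the open-ended Combo Target course after Baseline 3.

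The omission looks unintended. Table 101 lists 8-weekly visits for Arm B after Baseline 2, when patients receive the same Combo Target regimen. Other Arm C shells keep visits after Baseline 3: Table 60 (hematology) and Table 93 (vital signs) every 4 weeks, and Table 87 itself at week 4 and every 12 weeks.

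**Patients who could be affected.** Only those who start the final course can have such a visit, and the SAP does not give their number. Section 4.2 plans for at least 207 randomized patients in three arms, and 207 / 3 = 69. The range is therefore 0 to about 69 at the planned arm size.

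**Continuous ECG and ejection-fraction parameters (Section 21.3 against Tables 85-87)**

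- Section 21.3: PR + QT + QRS + QTcB + cardiac axis + ejection fraction = 6.
- Tables 85 and 86: PR displayed + 5 in the note = 6 of 6.
- Table 87: PR displayed + 0 from the note = 1 of 6, so 6 − 1 = 5 are missing. The note names 3 urinalysis items instead, all of which Table 84 already covers.

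No other shell gives a continuous summary of these five parameters for Arm C.

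**ECHO/MUGA label (Section 21.3 against Tables 88-90).** The third category is printed as 'Normal, CS' in 3 of 3 arms. The shells' footnotes define CS as clinically significant, so the label contradicts itself as well as Section 21.3.

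**The case against.** The strongest reply is that these are three editorial slips. Section 24.1 does not say that the shells override the SAP text, and Sections 21.3 and 23.2 state the correct parameters, categories and visit rule. A request for urinary red cells and bacteria under an ECG title is plainly a paste error that a competent programmer should query. That is fair, and it is why the repair is cheap. But the shells are the stated specification, and a visit list that simply ends early gives a programmer much less reason to ask.

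A reader might infer that Arm C would look safer. The documents do not support this:

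- The ECHO/MUGA label is the same in every arm, so it cannot favour one.
- A missing QT or ejection-fraction summary prevents a comparison; it does not display a lower risk.
- Table 90 still tabulates the Arm C ECG result, its clinical significance and the ECHO/MUGA interpretation at each visit.
- The adverse event tables (Section 21.1) count all reported events by arm with no restriction to a treatment phase, so a skin cancer reported as an adverse event in the final course would appear there.
- Listings 31, 32 and 37 keep the individual ECG, ejection-fraction and dermatology records.

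These outputs limit the harm but do not replace the planned summaries. A normal/abnormal count is not a change in QTcB or ejection fraction, and a listing is not a summary by arm.

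One caveat stands in full. Section 23.2 attributes the dermatology schedule to the protocol, each arm has its own schedule table there, and the protocol is not among the documents reviewed. Whether 8-weekly examinations are scheduled for Arm C after Baseline 3 must be confirmed against that table.

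**Conclusion.** The contradictions are real and should be removed before programming. Followed literally, the shells give an incomplete safety summary for Arm C: possible under-tabulation of skin findings, in the dermatology table only, for one of three treatment phases; and no summary of five of six ECG/ejection-fraction parameters. They also mislabel one safety category in all three arms. Efficacy analyses are untouched.

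The conclusion rests on two assumptions: that the shells are programmed as written, as Section 24.1 indicates, and that the general rule in Section 23.2 applies to Arm C after Baseline 3. The number of patients behind the dermatology gap is unknown, with the planned arm size of about 69 as its ceiling.

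**What to change.** - **Table 102:** add the 8-weekly visits after Baseline 3, in line with Section 23.2, after checking the Arm C schedule of assessments in the protocol. If that schedule has no such visits, Section 23.2 should state the exception instead.
- **Table 87:** replace the programmer note with the one in Tables 85-86, which names QT, QRS, QTcB, cardiac axis and ejection fraction.
- **Tables 88-90:** relabel 'Normal, CS' as 'Abnormal, CS'.

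The cost is one check of the protocol schedule and a few lines of shell text. Data collection, patient management and efficacy analyses do not change.
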